Cardiomyopathy; significant arrhythmias; blood pressure $>140/90$ mmHg; coronary disease; diabetes; other neurological disease; renal disease; cancer; recent weight change \geq 15 pounds; regular use of tobacco; intrathecal baclofen pump; grade 2 or greater pressure ulcers at erlevant contact site; peripheral nerve compressions or rotator cuff tears that limit the ability to exercise; history of bleeding disorder; current use of cardioactive, tricyclic antidepressants (amitriptyline, timipramine), other sedating agents; suicidal ideation; pregnant and/or breastfeeding women.

In addition, subjects must have no known hypersensitivity to buspirone hydrochloride and must not be taking a monoamine oxidase inhibitor. Subjects taking midodrine to treat hypotension will be allowed to participate in this study.

IV. SUBJECT ENROLLMENT

The Principal Investigator who is a Doctoral level physiologist with over 20 years of experience in performing these types of physiologic studies in humans will obtain consent during the first visit to the laboratory. Participants will be sent the consent form at least a week in advance so they have ample time to read and ask questions. Participants are encouraged to ask questions and are reminded that participation is strictly voluntary and will not affect their current or future care at Spaulding Rehabilitation Hospital or any of its affiliates.

V. STUDY PROCEDURES

Study design

A double-blind placebo controlled cross-over study in 20 individuals with high-level SCI will be performed to compare ventilatory responses after administration of placebo or 30 mg buspar. Ventilatory responses to a CO₂ rebreathing test and a bout of moderate to high intensity exercise will be assessed. In addition, an evaluation of sleep quality will be performed prior to, and following each drug phase.

Specifically, after two weeks of daily administration of buspar (dosing: starting at 15 mg 1 time a day for 2 days and increasing to 30 mg (15 mg in the morning and 15 mg at night) or placebo.

Subjects will also taper off the full dose of buspar by taking Buspar (15mg) 1 time a day for 2 days at the end of the two weeks. Ventilatory responses to a CO₂ rebreathing test, a bout of moderate to high intensity exercise, and sleep will be assessed again at the end of each two weeks phase.

Detailed procedures

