Once recruited for the study, the volunteers will visit the laboratory for a health screening session to further determine eligibility, obtaining informed consent, detailed health history, and set-up for an at home sleep over night evaluation. The following da a three-hour session (Visit 1) includes resting pulmonary function test, resting heart rate and blood pressure, height and weight, as well as a baseline CO₂ rebreathing test and a maximal incremental arm crank exercise test to determine maximal workload and aerobic capacity.

[figure not shown]
After volunteers complete the screening process, they will return for two visits to investigate the effect of buspirone or placebo on ventilatory responses (cross-over design, please see Figure 1).

These two study visits will take approximately 3 hours to complete and will be 14 days apart.

The sessions will be similar to the initial sessions but with a resting pulmonary function test and blood pressure preceding the CO₂ rebreathing and arm-crank tests. Following each of these segments an over night sleep assesment will also be performed.

The study sessions will take place at Spaulding Hospital Cambridge under the direct supervision of Cardiovascular Research Laboratory with a responsible physician on site, aware that the exercise session is taking place and readily available via pager or telephone if complications arise. This medical coverage falls into the "Physician Coverage" category as per the approved Spaulding Rehabilitation Hospital Policy and Procedure "General Safety Precautions and Procedures for the Conduct of Human Research."

Figure 1: Study schema

Pre-screening procedures

All study subjects will be preliminarily screened over the telephone to ensure that they meet preliminary eligibility requirements. Subjects who meet preliminary eligibility criteria and are interested in participating will be sent the informed consent letter at least one week before the first visit.

Screening & at home sleep evaluation

Informed consent will be obtained at Spaulding Rehabilitation Hospital, Cambridge. Subjects will be screened to ensure they meet preliminary eligibility criteria. All subjects will undergo a clinical interview to determine the presence of any medical disorders.

The following study assessments will be completed:

- Sleep Evaluation

Visit 1: Baseline Evaluation Visit

The following study assessments will be completed:

- Height and Weight

- Resting blood pressure and heart rate

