- Pulmonary function test
- CO₂ rebreathing test
- Maximal arm-crank exercise test

Visit 2 & 3: Laboratory Testing Visit

The second and third laboratory visits will be separated by fourteen days. All subjects will be instructed to abstain from vigorous exercise for 2 days prior to avoid muscle fatigue as well as autonomic and neuroendocrine effects of exercise, and instructed to refrain from caffeine and alcohol for the previous 24 hrs.

Distribution of Study Medication at the end of visit 1 and 2

After initial screening testing measures are complete, study medication (Buspar/Placebo) will be distributed to all volunteers by a study physician. Participants will be instructed as to how to take the medication dose. The initial dose of buspirone will be 15 mg daily (for two days) and will be increased by 15 mg to a dose of 30mg/day (15 mg in the morning and 15 mg iat night) with a 2-day 15 mg daily taper at the end of the two weeks.

Follow-up between visit 3 1-2 and 4 2-3: Adverse Event Monitoring (Telephone) day

Study staff will check in with study participants over the telephone at one week intervals to monitor any side effects or adverse events of the medication. If subjects are experiencing intolerable side effects, they will be taken off of the medication while completing the remaining study procedures. Participants will be informed that they may call study staff directly to report any side effects or adverse events at any time during the study.

Parameters to be measured

- Resting blood pressure and heart rate
- Pulmonary function test
- CO₂ rebreathing test
- Arm-crank Maximal exercise test
- Sleep Evaluation

Measurements

1) Pulmonary function test and resting blood pressure

Standard measurement of resting brachial arterial blood pressure and heart rate (electrocardiogram) will be performed.

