Sample size is based on previous data from our laboratory. We used mean and standard deviation of peak ventilation during arm crank exercise in individuals with low and high level SCI (Battikhia

et al. 2014). We assume that Buspirone would increase peak ventilation by 35% in humans, though to our knowledge, there is no reference available on the ventilatory effect of Buspirone in individuals with SCI. Thus, with a highest SD of 8.3 L/min, we expect that peak ventilation during arm crank ergometer exercise in high level individuals with SCI will be increased from 31.3 L/min at baseline to 42.1 L/min with buspirone, as compared with no change in the placebo-controlled group. With an a p level of 0.05 and a power of 80%, the sample size calculation indicates that we need at least 9 participants per group. Anticipating 10% drop out, we will need 10 participants per group, for a total of 20 participants.

Statistics

These projects will employ typical/appropriate statistical approaches to compare changes within and between groups. Statistical significance will be set at 0.05, and power at 80%. Statistical tests, conformity of the data to required statistical assumptions (e.g., normal distribution) will be verified using standard methods (e.g., Kolmogorov-Smirnov statistics and Q-Q plots). If assumptions for parametric tests do not hold, non-parametric alternatives will be employed. Correlations between variables will be assessed when necessary by Pearson's or Spearman's coefficient depending on the normality of the variables. If significant relations are found, appropriate regression analyses will be employed.

VII. RISKS AND DISCOMFORTS

Moderate risks are associated with exercise (arm-crank) testing. Some discomfort and feeling of fatigue will be experienced during these tests. There are other risks associated with these tests including abnormal blood pressure responses, fainting, irregular, fast or slow heart rhythm, and in rare instances, heart attack, stroke, or death. Wearing the mouthpiece during the arm-crank exercise testing may cause feelings of claustrophobia. Exercise testing may also induce some muscle or joint discomfort when and could result in tendonitis and/or musculoskeletal injuries. There is some discomfort with the lancet used on the finger for lactate measurement.

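### The sample size is calculated for two separate groups but the trial is a crossover, so the stated 80% power and 9 per group do not describe it; for peak exercise ventilation the error is conservative if the within-person correlation is 0 or more and both periods are usable

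*Combined protocol and SAP*

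**What the plan says.** Section V (Study design) sets the design: "A double-blind placebo controlled cross-over study in 20 individuals with high-level SCI will be performed". Under Detailed procedures, once screening is complete, "they will return for two visits to investigate the effect of buspirone or placebo on ventilatory responses". The dispensing subsection is headed "Distribution of Study Medication at the end of visit 1 and 2", so each participant receives a supply for both periods.

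Section VI (Sample Size) is written differently. On the source of its inputs it says: "We used mean and standard deviation of peak ventilation during arm crank exercise in individuals with low and high level SCI". It assumes a 35% rise with buspirone, from 31.3 to 42.1 L/min, "as compared with no change in the placebo-controlled group", and takes the highest SD, 8.3 L/min. At a level of 0.05 and 80% power it reports a minimum of 9 per group, and then: "Anticipating 10% drop out, we will need 10 participants per group, for a total of 20 participants". On the 35% it adds, "though to our knowledge, there is no reference available on the ventilatory effect of Buspirone in individuals with SCI".

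The Statistics paragraph says: "These projects will employ typical/appropriate statistical approaches to compare changes within and between groups". No within-person SD or correlation is given anywhere in the documents.

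**The concern.** In a crossover each participant serves as his or her own control. The precision of the treatment comparison is set by the SD of the within-person difference and by the total number of completers. The Sample Size paragraph uses neither. Its comparator is a separate group, its SD is the spread between people, and its total comes from doubling a per-group number.

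The 80% and the 9 per group are the only justification of the sample size in the documents. If they belong to another design, the reader does not know what power this trial has or what difference it can detect. The detectable difference matters here because the paragraph itself says that it has no reference for the assumed effect.

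**Working it through.** **Inputs from section VI.** Difference 42.1 − 31.3 = 10.8 L/min (34.5% of 31.3; exactly 35% would be 10.955). SD 8.3 L/min. Level 0.05, sidedness not stated; two-sided is assumed below. Power 80%. Dropout 10%, so 20 × 0.9 = 18 completers.

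**Assumptions not in the documents.** The within-person correlation, rho, is shown over a range. The SD is 8.3 L/min on each treatment, both periods are used, and there is no carryover.

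**Step 1: the plan's own figure.** For two independent groups, by normal approximation,

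n per group = 2 × (1.960 + 0.842)² × 8.3² / difference².

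This gives 9.27 at 10.8 L/min and 9.01 at 10.955 L/min, close to the stated 9. Then 9 / 0.9 = 10, and 2 × 10 = 20. The match is approximate: both values round up to 10, and a two-sided t-test needs 11 per group.

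**Step 2: precision of the crossover.** SD of the difference = 8.3 × √(2(1 − rho)), and standard error = that SD / √18. For 9 v 9 the standard error is 8.3 × √(2/9) = 3.91 L/min. The ratio of the two is √((1 − rho)/2), which is 0.71 at rho 0 and smaller at higher rho. A period-adjusted crossover analysis with 18 completers and a 9 v 9 t-test both have 16 degrees of freedom. For rho of 0 or more, the crossover therefore has more power at every true effect.

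**Step 3: power** (noncentral t, 16 df, 18 people in each row).

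| Design | SD of difference | Standard error | Power at 10.8 | Power at 8.1 | Power at 5.4 | Detectable at 80% (L/min) |
|---|---|---|---|---|---|---|
| Crossover, rho 0 | 11.74 | 2.77 | 95.5% | 78.5% | 45% | 8.3 |
| Crossover, rho 0.3 | 9.82 | 2.31 | 99.2% | 90.7% | 59% | 6.9 |
| Crossover, rho 0.5 | 8.30 | 1.96 | 99.9% | 97.3% | 74% | 5.8 |
| Crossover, rho 0.8 | 5.25 | 1.24 | >99.9% | >99.9% | 98% | 3.7 |
| Parallel, 9 v 9 | – | 3.91 | 73.6% | 49.4% | 25.5% | 11.7 |

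The detectable difference is 2.985 × the standard error at 16 df; for 9 v 9, 2.985 × 3.91 = 11.7. A plain paired t-test (17 df) barely changes the crossover rows: 95.7%, 99.2% and 99.9% at 10.8 L/min for rho 0, 0.3 and 0.5.

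**Step 4: could group mean treatment order?** With 18 completers, exactly 80% power at 10.8 L/min needs an SD of the difference of 15.35 L/min. Then rho = 1 − 15.35² / (2 × 8.3²) = 1 − 235.6/137.8 = −0.71. A strong negative correlation between two peak exercise tests in the same person is not plausible, so this reading does not recover the stated 80%.

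**Step 5: first period only.** The trial would become a parallel comparison, with power for 10.8 L/min of 73.6% at 9 v 9 and 78.6% at 10 v 10.

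**The case against.** **The arithmetic does not identify the method.** This is correct. A one-sided two-sample t-test at 10.8 L/min gives exactly 9 per group, and a paired calculation at rho 0.3 gives 9 people in total. The diagnosis rests on the comparator named, the SD used and the doubling to 20. The approximate numerical match only supports it.

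**The consequence is small.** Also correct. The total of 20 agrees with section V, section VIII calls this a pilot study, and power for the stated effect is higher than claimed.

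**Within-person comparison is not excluded.** The Statistics paragraph does mention changes within groups. But it does not specify the within-person treatment comparison, and it supplies no variance for one.

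**A reader might infer that the error is safe only if the full 10.8 L/min effect is real.** The figures do not support this. A smaller effect lowers power in any design: at 5.4 L/min the crossover has 45% to 74% for rho 0 to 0.5, against 25.5% for 9 v 9. That shortfall would come from an optimistic effect assumption, not from the two-group formula. It does not reverse the direction of the error.

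**A reader might infer that the second period will be lost.** The documents describe no washout between periods. They also give an elimination half-life of about 2 to 3 hours, a taper, and fourteen days between visits 2 and 3, and the study schema is not reproduced in the text available. None of this settles carryover, so the first-period figures remain a conditional scenario.

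**A reader might infer that 20 is too few for the hypercapnic response (Aim 1).** The paragraph gives no inputs for that outcome, so nothing can be concluded about it either way.

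**Conclusion.** The stated 80% power and 9 per group belong to a comparison of two independent groups and do not describe this crossover. For peak exercise ventilation the mismatch is conservative at any given effect, provided rho is 0 or more and both periods are usable: about 95.5% to 99.9% power for 10.8 L/min over rho 0 to 0.5, against the 80% stated. These figures rest on 18 completers, a two-sided 0.05 level, 8.3 L/min applying on each treatment, no carryover, and a correlation that the documents do not supply.

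The planned number is not shown to be too small for this outcome. This is a minor correction of the stated justification.

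**What to change.** Keep enrolment at 20 and rewrite the Sample Size paragraph, for example:

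> Twenty participants will each receive both treatments. The calculation concerns the within-person difference in peak exercise ventilation between buspirone and placebo and assumes no carryover. With 18 completers, a two-sided level of 0.05 and an SD of 8.3 L/min on each treatment, the SD of the difference is 8.3 × √(2(1 − rho)), where rho is the within-person correlation. Power for a difference of 10.8 L/min is about 95.5% at rho 0 and 99% at rho 0.3. The difference detectable with 80% power is about 8.3, 5.8 and 3.7 L/min at rho 0, 0.5 and 0.8.

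If the laboratory has its own repeat-test correlation, use it in place of the range. Remove the reference to a placebo-controlled group, and either drop per group or define the groups as the two treatment orders. In the Statistics paragraph, name the within-person treatment comparison to which the figures refer. The sponsor should confirm whether that is a paired t-test or a period-adjusted analysis; the figures are nearly the same for both.

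The cost is one rewritten paragraph and one added sentence. Enrolment and visits do not change.

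### The sample-size statement is written for separate buspirone and placebo groups, but the design is a cross-over, so the stated 80% power does not describe this trial and the paired analysis is left unnamed

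*Combined protocol and SAP*

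**What the plan says.** Section V (Study design) sets out the design: "A double-blind placebo controlled cross-over study in 20 individuals with high-level SCI will be performed". The ventilatory tests and sleep "will be assessed again at the end of each two weeks phase". Later parts of Section V agree. Detailed procedures calls the two study visits a cross-over, and medication is handed out at the end of Visit 1 and again at the end of Visit 2. Each person therefore supplies one set of results on buspirone and one on placebo.

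Section VI (Sample Size) describes something else. Peak ventilation "will be increased from 31.3 L/min at baseline to 42.1 L/min with buspirone, as compared with no change in the placebo-controlled group". At a significance level of 0.05 and 80% power, "the sample size calculation indicates that we need at least 9 participants per group". After a 10% allowance for drop-out, "we will need 10 participants per group, for a total of 20 participants". The SD used is 8.3 L/min, taken from the laboratory's earlier data on people with low and high level injury. It is not described as an SD of within-person differences, and no within-person correlation is given.

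Section VI (Statistics) then gives the comparison in one sentence: "These projects will employ typical/appropriate statistical approaches to compare changes within and between groups". Neither section names a paired test or a period term.

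**The concern.** A cross-over has no placebo group; it has 20 people, each observed on both treatments. Section VI counts people by treatment and adds the two counts, which is right only if different people receive each treatment. Two things follow.

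First, the stated power belongs to another design. A reader of Section VI would conclude that 20 people can just detect a 35% rise. In the cross-over, 20 people can detect a good deal less than that. This matters because the plan itself says that no reference exists for the ventilatory effect of buspirone in spinal cord injury, so the 35% is an assumption and a smaller effect would still be of interest.

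Second, the groups in the Statistics sentence are undefined, and the only groups that Section VI describes are treatment groups. An analyst who followed it in that sense would compare buspirone values with placebo values as if they came from different people, and would discard the pairing that the design provides.

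**Working it through.** **Inputs from Section VI:** means 31.3 and 42.1 L/min, so a difference of 10.8; a 35% rise, so 0.35 × 31.3 = 10.955; SD 8.3; alpha 0.05; power 80%; drop-out 10%. **Assumed, because the documents do not give them:** a two-sided test; within-person correlation ρ, varied from 0 to 0.8; equal correlation between visits; balanced treatment orders; no carry-over.

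**1. Reproduce the plan's figure.** For two independent groups, n per group = 2(1.96 + 0.84)² × 8.3² / d².
- d = 10.955: 9.01 per group.
- d = 10.8: 9.27 per group.
- Drop-out: 9 / 0.9 = 10 per group, 20 in total.

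The figure reproduces to rounding. With a two-sided t test at 10.8 L/min, power is 74% with 9 per group and 79% with 10. (A one-sided t version gives exactly 9 per group. The documents do not say which variant was used, but each is a separate-groups calculation.)

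**2. Same inputs in the stated design.** The SD of a within-person difference is 8.3 × √(2(1 − ρ)). Power uses the noncentral t distribution with n − 2 degrees of freedom, which allows for a period term. The detectable difference at 80% power is λ × SD of difference / √n, with λ = 2.984 for n = 18 and 2.963 for n = 20.

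| ρ (assumed) | SD of difference | Completers needed in total for 10.8 L/min | Detectable, 18 completers | Detectable, 20 completers |
|---|---|---|---|---|
| 0 | 11.74 | 12 | 8.3 | 7.8 |
| 0.5 | 8.30 | 8 | 5.8 | 5.5 |
| 0.7 | 6.43 | 6 | 4.5 | 4.3 |
| 0.8 | 5.25 | 5 | 3.7 | 3.5 |

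Two separate groups of 10 would detect 11.0 L/min, and 11.0 / 31.3 = 35%.

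**3. Power of this trial at its own effect.** With 10% drop-out, 20 × 0.9 = 18 complete. At ρ = 0 the noncentrality is 10.8 / (11.74 / √18) = 3.90 on 16 degrees of freedom, giving 95.5% power. Any positive correlation raises it.

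**4. Could the counts mean people per treatment order?** That would be 18 completers in a cross-over, which has at least 95.5% power for ρ of 0 or more. Reaching only 80% with 18 would need ρ of about −0.7. The normal formula for a cross-over at ρ = 0 also returns 9.27, but as people in total, which would not then be doubled.

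**5. Cost of an unpaired analysis, if one were run.** Under equal correlation, change from Visit 1 has the same SD as the within-person difference. With 20 completers the half-widths of the 95% interval are:
- period-adjusted paired: 2.101 × SD of difference × √(1/20);
- unpaired: 2.024 × SD of difference × √(2/20).

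Their ratio is √2 × 2.024 / 2.101 = 1.36, whatever ρ is. At ρ = 0.7 the half-widths are 3.02 and 4.12 L/min. The point estimate is the same in both.

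**The case against.** The strongest reply is that nothing is at risk at the plan's own effect. Twenty people in a cross-over exceed 80% power for 10.8 L/min at any non-negative correlation, and Section VIII calls this a pilot study, where a brief analysis section is common. This stands. A reader might infer that the trial is too small; the arithmetic shows the opposite.

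A reader might also infer that the plan commits to an unpaired test. It does not. The Statistics sentence names no test, includes comparison within groups, and leaves room for a sound paired analysis. The 1.36 ratio is therefore conditional on one reading of that sentence. Even then the error is conservative: wider intervals and no bias. In a paired analysis Visit 1 cancels, so change from Visit 1 and end-of-phase values give the same contrast. What remains is that Section VI gives the analyst no pointer to pairing and describes only treatment groups.

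A third tempting reading is that the sleep schedule contradicts itself. Study design says "an evaluation of sleep quality will be performed prior to, and following each drug phase", and Detailed procedures says "Following each of these segments an over night sleep assesment will also be performed", in addition to the study at screening. A study that follows phase 1 also precedes phase 2, so the two statements agree. No section names change across each phase as the sleep analysis, so no bias can be charged to the plan on that account.

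**Conclusion.** The point holds for the sample-size statement. Its count and its 80% power come from a two-independent-groups calculation and do not describe a cross-over in which 20 people each take both treatments. The correct description is more favourable: at least 95.5% power for 10.8 L/min with 18 completers, or a detectable difference of 8.3 down to 3.7 L/min as the correlation goes from 0 to 0.8. These figures rest on the plan's SD of 8.3 being the SD of single values at a visit, a two-sided 5% test, balanced orders and no carry-over. The correlations are assumptions. If 8.3 were instead the SD of within-person differences, the row for ρ = 0.5 would apply.

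For the analysis sentence the point is narrower: a paired, period-adjusted comparison is permitted but not named. This is an inexpensive improvement to the text, not a flaw that threatens the trial. Carry-over, and the timing of the taper relative to end-of-phase testing, are separate points; on the taper, the passages need only be reconciled.

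**What to change.** Keep 20 participants.

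**Sample Size.** Remove the per-group counts and the reference to a placebo group. State the SD, the test and the design, and give the detectable difference over a range of correlations, for example:

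> Each participant receives both treatments. With 18 completers of 20 (10% drop-out), SD 8.3 L/min and a two-sided 5% test with a period term, the trial has 80% power to detect a difference in peak ventilation of 8.3, 5.8, 4.5 or 3.7 L/min if the within-participant correlation is 0, 0.5, 0.7 or 0.8 (7.8, 5.5, 4.3 or 3.5 L/min if all 20 complete).

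**Statistics.** Replace the sentence on changes within and between groups with:

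> The treatment effect is the within-participant difference between end-of-phase values on buspirone and on placebo, estimated with treatment and period as fixed effects (a mixed model or an equivalent period-adjusted paired analysis). Neither the Visit 2 tests nor the sleep study at the end of phase 1 is used as a baseline for phase 2.

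The last sentence is needed because those measurements are themselves outcomes of phase 1.

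**Cost.** Wording only, with no change in sample size or visits. The period term uses one degree of freedom, which is negligible with balanced orders. The loss of power is larger only if treatment orders turn out unbalanced.

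### Regression is triggered by a significant correlation, so with 18 to 20 people the exploratory slopes that get fitted are selected for size

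*Combined protocol and SAP*

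**What the plan says.** All the relevant text is in Section VI, Statistical Analysis, apart from the design statement.

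- On associations: "Correlations between variables will be assessed when necessary by Pearson's or Spearman's coefficient depending on the normality of the variables". The variable pairs are not named.
- On regression, in the next sentence: "If significant relations are found, appropriate regression analyses will be employed". The models are not named, and nothing is said about how non-significant associations will be reported.
- On the threshold: "Statistical significance will be set at 0.05, and power at 80" per cent. Sidedness is not stated.
- On numbers: "Anticipating 10% drop out, we will need 10 participants per group, for a total of 20 participants". Section V, Study design, describes the same 20 people: "A double-blind placebo controlled cross-over study in 20 individuals with high-level SCI will be performed".

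**The concern.** A rule that fits a model only after a significance test on the same data filters the estimates. In a small sample the filter is coarse: a modest true association passes only when chance has made it look larger than it is. The fitted slope is then too large on average, and its nominal 95% interval can cover the truth less than 95% of the time.

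Many pairs could be examined. The Measurements part of Section V lists spirometry, several rebreathing variables, exercise gas exchange, lactate and sleep measures. With the pairs left open, some chance associations can be expected to pass, and the rule attaches a slope to each of them. What is at stake is how far a reader can trust any slope linking, say, the rebreathing response to exercise ventilation.

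**Working it through.** **Inputs.** From Section VI: significance level 0.05, 20 participants, 10% dropout. Assumed, because the documents do not say: a two-sided test, Pearson correlation, one observation per person, simple linear regression, standardised bivariate normal variables, and a range of true correlations from 0 to 0.6.

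**Step 1. The plan's own number of people.** The sample-size text uses an SD of 8.3 L/min and a rise from 31.3 to 42.1 L/min, a difference of 10.8. The two-group normal approximation gives

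n per group = 2 × [8.3 × (1.960 + 0.842) / 10.8]² = 9.27,

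which rounds up to 10; the plan states at least 9, so its figure is reproduced to within one participant. Then 9 / (1 − 0.10) = 10 per group, 20 in total, as stated. With 10% lost, 20 × 0.90 = 18 remain. The calculation treats the arms as parallel groups although the design is a cross-over, but that does not matter here: 20 people are enrolled either way.

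**Step 2. The threshold that the rule implies.** A correlation is significant when |r| exceeds t / √(n − 2 + t²), where t is the 97.5% point of Student's t on n − 2 degrees of freedom.

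- n = 20: t = 2.101, so |r| must exceed 2.101 / √(18 + 4.414) = 0.444.
- n = 18: t = 2.120, so |r| must exceed 2.120 / √(16 + 4.494) = 0.468.

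**Step 3. What passes.** Data sets of size n were simulated (200,000 per setting). The least-squares slope and its 95% interval were kept only where the correlation had p < 0.05. Results at n = 20:

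| True r | Share that pass | Mean passing slope ÷ true slope | Coverage of the 95% CI among those that pass |
|---|---|---|---|
| 0 | 5% | not defined; mean passing absolute r is 0.52 | 0% |
| 0.2 | 13% | 2.6 | 80% |
| 0.3 | 25% | 1.9 | 90% |
| 0.4 | 43% | 1.45 | 94% |
| 0.5 | 64% | 1.2 | 96% |
| 0.6 | 84% | 1.1 | 96% |

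At n = 18 the pattern is the same and slightly worse: at a true r of 0.3, 23% pass and the mean passing slope is 1.9 times the truth, with coverage of 89%.

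**Step 4. Is it the filter or the small sample?** When every slope was kept, coverage was 95% in every setting, and under a linear model the least-squares slope is unbiased. The distortion comes from the filter. The small sample only makes the filter coarse.

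**Step 5. Can a reader tell the cases apart?** At n = 20 the mean passing |r| is 0.52 when the truth is zero and 0.55 when it is 0.3. A passing result looks much the same in both.

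**The case against.** There are four fair points against this.

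- **The factor rests on an assumption.** The documents give no true correlation for any pair. A reader might infer that any reported slope would be badly exaggerated and that its interval would lose 95% coverage. The documents do not support that. From a true r of about 0.4 upward coverage is 94% to 96%, and at 0.6 the exaggeration is about a tenth. Nothing in the documents places the rebreathing and exercise responses at the weak end of the range. This point stands, which is why the whole range is shown.
- **The text does not say that regression is confined to significant correlations, or that the others go unreported.** A reader might infer planned suppression; the text leaves reporting unspecified. If every coefficient were published, readers would still see an unselected r for each pair. What survives is narrower: the plan states one trigger for a regression and no other, so the slopes and their intervals are selected even if the coefficients are not.
- **The analysis is peripheral.** Both specific aims concern the effect of buspirone on ventilatory responses. Correlations are optional, and the treatment comparison is untouched. This stands, and it sets the priority.
- **Pooling of visits is not planned.** The rebreathing and arm-crank tests are done at three visits, so a reader might infer that 60 points from 20 people would be correlated as if independent. That would raise the false-positive rate of a 5% test to about 14% to 24%, for assumed within-person correlations of 0.6 to 0.9. The plan does not say that visits will be pooled, so this is only a caution.

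A reader might also infer that a later trial would be planned on these slopes. Section VIII says only that this is a pilot and that more work may be needed, so that is conjecture.

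**Conclusion.** The point holds in limited form. The rule selects slopes for size at a threshold of |r| = 0.44 with 20 people, or 0.47 with 18. The consequence is roughly a doubling for a true r near 0.3, more below that, and little at 0.5 or above. When the true r is zero, every slope that passes is a false finding. These figures assume a two-sided Pearson filter, one point per person and a simple linear model; the true correlations are assumed, not taken from the documents. The issue is confined to the exploratory association analyses and does not bear on the buspirone–placebo comparison. Low priority.

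**What to change.** Replace the sentence that makes regression conditional on significance. In its place:

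1. List a few associations in advance, for example the buspirone-minus-placebo difference in rebreathing response against the same difference in exercise response.
2. State that each participant contributes one point to each association. This also closes off the pooling question.
3. State that every listed slope will be reported with its 95% CI, whether or not it is significant, and labelled exploratory.

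This costs a change of wording in the Statistics paragraph, with no added participants, visits or measurements. The only downside is that associations outside the list would have to be marked post hoc.
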